1.0 Objectives

1.1 Describe the purpose, specific aims, or objectives of this research.

Response:

Pilot Phase: The purpose of this phase is to conduct taste tests to determine children's reactions to foods that are being considered for the subsequent experimental phase.

Experimental Phase: The objective of this research is to make healthier kids' meal options more appealing and easier to choose via an in-restaurant intervention that combines repeated exposure and choice architecture strategies. This phase has 2 main aims:

Aim 1: To test effects of a healthier kids' meal intervention on children's meal orders.

Aim 2: To test effects of a healthier kids' meal intervention on children's dietary intake.

1.2 State the hypotheses to be tested, if applicable.

NOTE: A hypothesis is a specific, testable prediction about what you expect to happen in your study that corresponds with your above listed objectives.

Response:

Pilot Phase: There is no explicit hypothesis during this exploratory pilot phase.

Experimental Phase:

Hypothesis 1a: 4-to-8-year-old study participants in intervention restaurants will be more likely than controls to select one of the promoted healthier kids' meals at post-test.

Hypothesis 1b: 4-to-8-year-olds in the intervention group will order fewer calories and desserts and less saturated fat, sodium and sugar at post-test versus controls.

Hypothesis 1c: The promoted healthier meals will make up a greater percentage of kids' meals ordered in intervention restaurants versus controls, based on sales data across the study period.

Hypothesis 2: Compared to controls, 4-to-8-year-old study participants in the intervention group will consume fewer calories and less saturated fat, sodium, and sugar in the restaurant at post-test.

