Aim 2. We will use mixed models with linear distributions to compare study groups on calories, saturated fat, sodium, and sugar consumed in the restaurant, with study group, time point (initial, post), and the group-by-time interaction as fixed effects and a random effect for restaurant location. We will repeat these analyses using data from repeat 24-hour dietary recalls to examine intervention effects on daily energy, saturated fat, sodium, and sugar intake among participating children (post-test only). We will also explore associations between ordering of the promoted meals and children's dietary intake within the meal and total day and will repeat aforementioned models testing intervention effects on orders and intake, incorporating child sex, age, and weight status (overweight/obese vs. normal weight) as potential covariates and effect moderators. We will also plan ancillary analyses that explore dining at Anderson's locations besides the assigned location and number of exposures as additional factors in the mixed models described above; if there are substantial missing data on number of exposures, we can treat this variable as categorical with "missing" retained as a category, to retain our sample size. Finally, if substantial demographic differences between groups are revealed, we will incorporate propensity scores into our analyses to account for this potential source of bias. Analyses will incorporate multiple imputation methods as appropriate, depending on the extent of missing data.

17.2 If applicable, provide a power analysis.

NOTE: This may not apply to certain types of studies, including chart/records reviews, survey studies, or observational studies. This question is asked to elicit whether the investigator has an adequate sample size to achieve the study objectives and justify a conclusion.

Response:

Pilot Phase: No power analysis is required for this qualitative exploratory phase.

Experimental Phase: To determine the sample size needed to test effects on orders of healthier meals, we used findings from our preliminary research, showing that 27.8% of participants exposed to study placemats and 6.7% of the control group ordered the featured healthier entrees (1). Using these values, an alpha of .05,

power of 80%, 6 cluster, and an intraclass correlation of .01 based on prior restaurant research (2), it is estimated that 124 participants will be needed to test intervention effects on meal selection.

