Repeating this calculation for calories consumed in the restaurant (Aim 2), we used calories consumed among children ordering a healthier entrée (473.3 ± 197.4) or less healthy entrée (556.6 ± 199.4) in our preliminary research and the same alpha, power, intraclass correlation, and cluster values used above for an estimate of 684 participants ($d=.42$). To retain adequate power in the event that some recruited participants do not return at post-test, we increased this estimate by ~35%, a figure informed by show rates from prior restaurant research (3), for a final target sample of 930 families (465 per study group).

References:

17.3 Describe any procedures that will be used for quality control of collected data.

Response:

All data will be entered and quality controlled by trained staff. Data that are entered manually, which in this study includes entering data from study forms (experimental phase; e.g. plate waste measurements) will be double entered by study staff, with double entry compared and cleaned as needed.

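### The Aim 2 power calculation takes its effect size from children grouped by the entrée they ordered, not by arm, so 80% power at 684 has not been shown for the planned comparison

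*Combined protocol and SAP*

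**What the plan says.** Hypothesis 2 (Section 1.2) is about randomised groups: compared with controls, "study participants in the intervention group will consume fewer calories and less saturated fat, sodium, and sugar in the restaurant at post-test". The analysis plan in Section 17.1 matches it: "We will use mixed models with linear distributions to compare study groups on calories, saturated fat, sodium, and sugar consumed in the restaurant", with a random effect for restaurant location.

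The power analysis in Section 17.2 has two parts, both drawn from the preliminary randomised study (not this trial's taste-test Pilot Phase).

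- **Aim 1, meal selection.** The inputs are preliminary ordering rates by arm, "showing that 27.8% of participants exposed to study placemats and 6.7% of the control group ordered the featured healthier entrees". With 80% power, 6 clusters and an ICC of .01, this gives 124 participants.
- **Aim 2, calories consumed.** Here "we used calories consumed among children ordering a healthier" entrée (473.3 ± 197.4) or a less healthy one (556.6 ± 199.4), with "the same alpha, power, intraclass correlation, and cluster values used above for an estimate of 684 participants" and d=.42.

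The 684 is then raised by about 35% for non-return, giving the enrolment target of 930 families.

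**The concern.** The Aim 1 input is a contrast between arms. The Aim 2 input is a contrast between children who made different choices, whichever arm they were in. The trial will not test that contrast as its Aim 2 hypothesis; Section 17.1 lists the association between ordering promoted meals and intake only as something to explore. The documents give no between-arm calorie difference and no reason for using the entrée-choice gap in its place.

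A contrast by entrée ordered is normally larger than the contrast between arms that works through it, because some intervention children do not order the featured meal and some control children do. The Aim 1 paragraph shows this for the preliminary study: most children in both arms did not order the featured entrée.

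At stake is the stated 80% power for one of the trial's two main aims. The same input sets the 684, and through it the 930. Anyone judging the informativeness of the Aim 2 result would rely on a figure that belongs to a different comparison.

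**Working it through.** **Inputs, all from Section 17.2.** Means 473.3 and 556.6 kcal, SDs 197.4 and 199.4; alpha .05; power 80%; 6 clusters; ICC .01; preliminary ordering rates 27.8% and 6.7%. Section 4.1 gives three restaurants per arm. Sidedness is not stated; two-sided is assumed because it reproduces the plan's figure.

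**Step 1: reproduce d.** Gap = 556.6 − 473.3 = 83.3 kcal. Pooled SD = √[(197.4² + 199.4²)/2] = 198.4. So d = 83.3/198.4 = .420, as stated.

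**Step 2: reproduce 684.** With N children in 6 restaurants, m = N/6 and the design effect is DE = 1 + (m − 1) × .01. The noncentrality is d/√(4·DE/N), referred to a noncentral t with 6 − 2 = 4 df.

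- At N = 684: m = 114 and DE = 1 + 113 × .01 = 2.13.
- Standard error in SD units = √(4 × 2.13/684) = .1116.
- Noncentrality = .42/.1116 = 3.76, and power = 80.0%.

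The smallest N (in whole restaurants of equal size) reaching 80% is 684, an exact match. A normal approximation gives 252, a one-sided t with 4 df gives 324, and 5 df gives 522; none of these matches. So the formula is sound and the question is only what d represents.

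**Step 3: translate the entrée gap into an arm difference.** The documents do not do this, so a model is needed. Assume that (a) calories differ between arms only through entrée choice and (b) the 83.3 kcal gap is causal. Then

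arm difference = (uptake in intervention − uptake in control) × 83.3 kcal.

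Under (a) and (b), an arm difference of 83.3 kcal requires 100% uptake in one arm and 0% in the other. If also (c) the preliminary ordering rates apply, the uptake gap is 27.8 − 6.7 = 21.1 points and the arm difference is .211 × 83.3 = 17.6 kcal, d = 17.6/198.4 = .089. Noncentrality at 684 is .0886/.1116 = .79.

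**Step 4: power by uptake gap**, N = 684, method of Step 2, assumptions (a) and (b):

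| Uptake gap (points) | Arm difference (kcal) | d | Power |
|---|---|---|---|
| 10 | 8.3 | .042 | 6.0% |
| 21.1 (preliminary study) | 17.6 | .089 | 9.5% |
| 30 | 25.0 | .126 | 14.2% |
| 40 | 33.3 | .168 | 21.4% |
| 50 | 41.7 | .210 | 30.4% |
| 60 | 50.0 | .252 | 40.7% |
| 75 | 62.5 | .315 | 57.0% |
| 90 | 75.0 | .378 | 71.8% |
| 100 | 83.3 | .420 | 80.0% |

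**Step 5: sensitivity at the 21.1-point gap.** If all 930 families completed, power would be 10.2%. A normal approximation gives 12.5% at 684 and 13.5% at 930. With unlimited children in 6 restaurants the noncentrality tends to .0886/√(4 × .01/6) = 1.085, so power levels off at about 13% (t, 4 df) or 19% (normal). More children in the same restaurants would not rescue that scenario.

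**The case against.** The strongest reply is that the low figures are the reviewer's model, not the plan's. Much of that stands.

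- **The ordering rates are preliminary findings used to size Aim 1, not a forecast for this trial.** Section 3.1 says the trial aims to strengthen the preliminary effect by adding repeated exposure. Section 10.1 adds a diner card that, in the intervention arm, rewards only featured meals. The uptake gap could well exceed 21.1 points. The documents do not say by how much, or whether it lasts to post-test, when an earned free meal is of the family's choice.
- **Entrée choice need not be the only pathway.** Intervention restaurants promote whole meals and offer a toy in place of dessert, and Hypothesis 1b expects fewer desserts. This could add to the arm difference. At the preliminary uptake gap, though, other pathways would have to supply about 83.3 − 17.6 = 65.7 kcal averaged over all intervention children to reach the difference used, and Section 17.2 counts none of it.
- **The two inputs may not describe the same thing.** The 21.1 points concern featured healthier entrées; the 83.3 kcal contrasts healthier with less healthy entrées. The entrée contrast is also not randomised, so part of it may reflect who chooses what.
- **The preliminary study was randomised**, so the investigators may hold a between-arm calorie difference that the documents do not show.
- **Intake is a secondary outcome** (Section 2.1), and Aim 1 is stated to need only 124. But the Aim 2 calculation is the one that sets enrolment.

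A reader might go further and infer that Aim 2 has about 10% power, or that the plan itself expects an 18 kcal effect. The documents support neither: both need assumptions (a), (b) and (c) together. Nor is there an arithmetic error in the 684.

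What these replies do not supply is a reason why a gap between orderers and non-orderers should stand for a gap between arms.

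**Conclusion.** The effect size is the wrong contrast for the hypothesis and model it is meant to support, and this can be read directly from Sections 1.2, 17.1 and 17.2. The 684 and the 80% are correct for an arm difference of .42 SD (about 83 kcal), but nothing in the documents shows that such a difference between arms is expected. The stated power for Aim 2 is therefore unsupported.

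How far the true power falls short cannot be fixed from the documents. If entrée choice is the only pathway and the entrée gap is causal, every uptake gap short of 100 points leaves power below 80% at 684 completers under the method that reproduces the plan's number. It is about 10% at the preliminary gap and about 6% to 57% for gaps of 10 to 75 points. Under a normal approximation 80% would be reached at a gap of about 75 points, but that method would have given 252, not 684. Pathways outside entrée choice could raise all of these figures.

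**What to change.** Amend Section 17.2 as follows.

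1. Say that 684 completers in 6 restaurants, with an ICC of .01, give 80% power for a between-arm difference of about 83 kcal (.42 SD), and that this value comes from a contrast by entrée ordered, not by arm.
2. State the between-arm calorie difference that is expected at post-test and justify it, from the randomised arms of the preliminary study if those data are available. If an effect of the diner cards or the toy offer is counted, say how much and why.
3. Recompute power for 6 clusters at that difference, naming the test, its degrees of freedom and its sidedness.
4. Add the table of power over uptake gaps, with the 18 kcal row marked as a scenario and its assumptions listed.

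This changes wording only. Enrolment and the Aim 2 model stay as they are. The downside is that the stated power for Aim 2 is likely to become less favourable.

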Compensation. Participating families can receive up to \$300 for participating in the study (\$265 for all standard assessments; plus an additional \$35 if in the observed subsample). Families will receive up to \$50 for completing measures at the initial time point. Then, throughout the exposure period (midpoint), they can receive up to \$120: \$90 of the \$120 will be provided during the exposure period for completion of weekly online surveys (divided up and paid weekly), and an additional payment will be provided later for each of the weekly exposures indicated on their frequent diner card ($\$5 \times \text{number of exposures}$, max = 6; determined upon collection of the card at post-test). After the midpoint assessments, families will receive one more payment; this payment will be administered following post-test and will include up to \$50 for completion of in-restaurant post-test measures (final survey; intake measures used during their cohort – i.e., weighed plate waste and/or remote food photography), plus a \$20 bonus for following post-test procedures as instructed (i.e., turning in their frequent diner card at post-test if paper version; coming to originally-scheduled appointment time if in-person), \$25 for completion of the online dietary intake survey (ASA24), and the aforementioned midpoint payments from frequent diner card use. Families will also receive their free kids' meal at post-test if frequent diner cards are completed, and those randomly selected to be included in the observed subsample will receive an additional \$35. Children will receive a small prize (e.g., stickers) each time their frequent diner card is used. Payments will be made via a prepaid debit card provided by the study.

[figure not shown]

Figure 1. Data collection timeline for an individual cohort with main measures. These procedures will happen repeatedly over about 3-4 years to collect data from about 3-5 cohorts.

10.2 Describe what data will be collected.

NOTE: For studies with multiple data collection points or long-term follow up, consider the addition of a schedule or table in your response.

Response: Data collected are detailed below. In addition, please see attachments for corresponding forms/surveys with specific questions to be administered.

Pilot Phase: We will collect data on children’s liking of and preferences for the foods they taste during taste tests, as well as parent-reported demographics.

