17.0 Data Management and Analysis

17.1 *Describe the data analysis plan, including any statistical procedures. This section applies to both quantitative and qualitative analysis.*

Response:

Pilot Phase: Child feedback will be used to determine which food components will be used in the experimental phase.

Experimental Phase: Descriptive statistics, normality plots, and study group differences will be examined for all variables, with results informing analyses (e.g., using non-parametric statistics if appropriate). Planned analyses corresponding to each aim are described below. Analyses incorporate random effects for restaurant location as required in cluster-randomized trials.

Aim 1. A mixed model with a binomial distribution will test whether intervention children are more likely to order a healthier promoted meal compared to controls,

with study group, time point (initial, mid1-mid6, and post), and the group-by-time interaction as fixed effects, a random effect for restaurant location, and a contrast focused on study group differences at post. Mixed models with linear distributions will compare the groups on calories, saturated fat, sodium, and sugar ordered, with the same factors. We will use sales data and chi-square analyses to compare the percentage of kids' meals ordered that were healthier featured meals in intervention versus control restaurants across the study period and separately by recruitment, exposure, and redemption periods. We will also summarize child and parent orders at each time point and the frequency of behaviors of interest (e.g., who ordered for the child) during parent-child interactions in intervention and control groups and will compare the number of kids' meals ordered in each group of restaurants against initial sales data from parallel time periods one year prior, overall, by cohort, and by recruitment, exposure, and redemption periods.

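### The Aim 1 contrast at post-test rests essentially on families who return; the sample-size inflation protects its power but not against bias from who returns

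*Combined protocol and SAP*

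**What the plan says.** All references are to the combined protocol and SAP.

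- **Sample size (17.2).** The calorie calculation ends with "for an estimate of 684 participants". The plan continues: "To retain adequate power in the event that some recruited participants do not return at post-test, we increased this estimate by ~35" percent, giving 930 families, 465 per group.
- **Primary model (17.1, Aim 1).** Fixed effects are group, eight time points (initial, six midpoints, post) and their interaction. Restaurant location is the only random effect named. The test is "a contrast focused on study group differences at post". The linear models for calories, saturated fat, sodium and sugar ordered use the same factors.
- **Missing data (17.1).** "Analyses will incorporate multiple imputation methods as appropriate, depending on the extent of missing data". No threshold, imputation model, missing-data assumption or sensitivity analysis is given for the post-test order.
- **Cards and payments (10.1).** Intervention cards are marked only for the featured meals, control cards for any kids' meal. Besides the weekly survey money, "an additional payment will be provided later for each of the weekly exposures indicated on their frequent diner card", with the amount settled when the card is seen at post-test. A completed card earns a free kids' meal, redeemed in the post-test period.
- **Orders before post-test (10.1, 10.2).** Orders are also asked about in the weekly online survey during the exposure period, so they do not require a post-test visit. Section 20.3 allows data already given by withdrawn families to be kept and analysed.

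**The concern.** Hypotheses 1a and 1b concern the post-test order, and a family that does not come back has none. A mixed model over repeated measurements often copes with this, because a child's earlier values help predict the missing one. That works only if the model links measurements within a child, and the model as written does not.

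The gap matters because the reason to return is not the same in the two arms. In the intervention arm, the per-mark payment and the free meal depend on having ordered featured meals. In control they depend on having ordered any kids' meal. Intervention children who took up the featured meals may therefore be more likely to be scored at post-test, with no matching selection in control. The contrast could then show a difference although post-test ordering among all enrolled children is the same in both arms. A larger sample does not correct that.

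**Working it through.** **1. Reproduce the plan's figures.** Inputs from 17.2: "Using these values, an alpha of .05"; "power of 80%, 6 cluster, and an intraclass correlation of .01 based on prior restaurant research (2"); and "calories consumed among children ordering a healthier entrée (473.3 ± 197.4) or less healthy entrée (556.6 ± 199.4").

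- d = (556.6 - 473.3) / sqrt((197.4² + 199.4²)/2) = 83.3/198.4 = 0.42.
- Three restaurants per arm, two-sided test (sidedness is not stated), noncentral t with 4 degrees of freedom: 114 children per restaurant give power 0.800, so N = 6 × 114 = 684. This matches.
- 684 × 1.35 = 923.4; the exact factor is 930/684 = 1.36. This is consistent with the stated approximate 35%.

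**2. Implied allowance for non-return.** 930 - 684 = 246, and 246/930 = 26.5%. The 35% is an addition to 684, not a loss rate; a 35% loss would leave about 604 of 930.

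**3. Do non-returners' earlier orders reach the post contrast?** This was checked on a linear stand-in: 6 restaurants × 155 children, 8 time points, saturated group-by-time terms, child SD 1, residual SD 1 and a true post effect of 0.40. Return was related to midpoint values in the intervention arm only, with about 25% (control) and 30% (intervention) missing. Means are over 40 replicates.

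| Estimate of the post contrast | Result |
|---|---|
| True value | 0.40 |
| Raw difference among returners | 0.69 |
| Model as written (restaurant effect only) | 0.69 |
| Same model plus a child random intercept | 0.42 |

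Shifting intervention non-returners' midpoint values by a full residual SD moved the as-written contrast by at most 0.011. With a child intercept it moved by about 0.23. The model as written is in effect a comparison of returners. The 0.69 reflects the selection built into this example and is not a forecast for the trial.

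**4. Possible size for the yes/no outcome.** The documents give no return rates by number of marks, so these are assumptions:

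- no true arm difference at post and 26.5% loss overall;
- control loss unrelated to orders;
- intervention return rising from about 63-68% (no marks) to 83-88% (six marks), or from 58-65% to 88-95%;
- one underlying propensity per child (logit SD 1 to 2) driving both the exposure-period and post-test orders;
- 400,000 simulated children per scenario.

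The standard error at equal rates, with 342 completers per arm and design effect 1 + 113 × 0.01 = 2.13, is sqrt(2p(1-p) × 2.13/342).

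| Post rate p, both arms | Spurious excess (points) | SE (points) | Excess / SE |
|---|---|---|---|
| 6.7% | 0.3-1.2 | 2.8 | 0.11-0.43 |
| 15% | 0.5-2.2 | 4.0 | 0.13-0.55 |
| 27.8% | 0.9-3.3 | 5.0 | 0.18-0.66 |

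The excess is smaller still if featured uptake during exposure is low.

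**5. Does the order history help?** With all six midpoint orders known, standardising the post order over that history within the intervention arm brought the error to within 0.1 point. That success is partly built in, because return was generated from those same orders. With only the first two surveys available, roughly 25-65% of the bias remained.

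**The case against.** Several points on the other side stand.

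- **Most of the cash for returning is the same in both arms.** Section 10.1 pays at post-test up to $50 for measures, $20 for following procedures and $25 for the dietary recall. That is $95 regardless of arm or marks, against at most 6 × $5 = $30 for marks plus one kids' meal. This limits the asymmetry without removing it.
- **The direction is not settled.** A reader might infer that the contrast must overstate the effect. The documents do not support that. The reward is a free kids' meal of the family's choice (4.1), redeemed at the scored visit. Children with full cards may spend it on a non-featured meal, which could weaken or reverse the bias. The simulation did not examine this.
- **The plan does not forecast losing a quarter of families.** That reading is tempting, but 17.2 describes a contingency; 26.5% is what the target accommodates.
- **The plan does not exclude the weekly orders from imputation.** It is silent on the imputation model. Nor does it say that outcomes by arm will be seen before deciding; the extent of missingness can be judged without them.
- **The size is modest.** The largest excess, 3.3 points, compares with a planned difference of 27.8 - 6.7 = 21.1 points and puts both arms at 27.8%.

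None of this supplies the missing link between a child's earlier orders and the post contrast, or a rule for when to impute.

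**Conclusion.** The point holds, as something the analysis plan should correct before analysis. It follows from the text that the inflation addresses power only, that the model as written draws the post contrast essentially from returners, and that part of the reward for returning depends on featured ordering in one arm only.

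That this produces bias is conditional: featured ordering during exposure must predict both return and the post-test order. Upward bias is then the likelier direction, but not assured. The size, 0.3 to 3.3 points or roughly 0.1 to 0.66 standard errors, rests on assumed return gradients. It is unlikely to create the planned effect by itself, but could matter for a smaller true effect. The documents do not support a claim that the primary result will be invalid.

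**What to change.** In 17.1, state that the primary post contrast uses the order history of all enrolled families, whatever the extent of missingness.

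- **Preferred.** Multiple imputation of missing post-test orders, separately by arm. The imputation model includes restaurant, the initial order and the six midpoint survey orders, plus electronic card records where available. Section 10.2 indicates that electronic cards can be confirmed from study records, and Table 1 lists card data at midpoint, so those marks need not depend on a post-test visit.
- **Acceptable alternative.** Add a child-level random effect to the Aim 1 models, so that each child's earlier orders inform the post contrast.
- **Sensitivity analyses.** Keep the restaurant-only, returners-only model. For the yes/no outcome, add an analysis that counts every missing post-test order as not featured in both arms. At the planning rates with equal 26.5% loss, this would turn 21.1 points into 0.735 × 21.1 = 15.5.

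The cost is wording and some programming; the weekly surveys are already planned, so no new data are needed. The downside is that the result then depends on the imputation or random-effect model. Survey completion among non-returners is not stated, and where they also lack midpoint surveys the fix reduces the bias rather than removing it. The number of midpoint surveys available for non-returners should be reported by arm.
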